**Exclusion Criteria:**

1. Pregnant or lactating females; lactating females must agree to discontinue nursing before the IMPs are administered. WOCBP must have a negative pregnancy test at Screening and Day 1.
2. Past 2 years history of alcohol abuse or current significant alcohol consumption ( >7 drinks per week for males or female; 1 drink = 12 ounces of beer (5% alcohol); 5 ounces of wine (12% alcohol), and 1.5 ounces of 80 proof distilled spirits (40% alcohol) ).
3. LDL-C  $\geq 190$  mg/dL and already on a stable dose of statin and/or proprotein convertase subtilisin/kexin type 9 (PCSK9) inhibitor for  $\geq 30$  days at Screening.
4. Renal dysfunction or nephritic syndrome or a history of nephritis or chronic kidney disease, including estimated glomerular filtration rate (eGFR) (using central laboratory determined Chronic Kidney Disease Epidemiology Collaboration [CKD-EPI] equation) <60 mL/min/1.73 m^2 at Screening.
5. Recent (within 6 months prior to Screening or between Screening and Randomization) myocardial infarction (MI), unstable angina leading to hospitalization, uncontrolled, symptomatic cardiac arrhythmia (or medication for an arrhythmia that was started or dose changed within 3 months of Screening), coronary artery bypass graft surgery (CABG), percutaneous coronary intervention (PCI), carotid surgery or stenting, cerebrovascular accident, transient ischemic attack (TIA), endovascular procedure or surgical intervention for peripheral vascular disease, or plans to undergo a major surgical or interventional procedure (e.g., PCI, CABG, carotid or peripheral revascularization). Subjects with

implantable pacemakers or automatic implantable cardioverter defibrillators may not be considered.

6. Uncontrolled hypertension, defined as sitting systolic blood pressure (SBP)  $\geq 160$  mmHg and/or diastolic blood pressure (DBP)  $\geq 100$  mmHg after sitting quietly for 5 minutes at Screening.
7. Type 1 diabetes or uncontrolled T2DM including  $HbA_{1c} \geq 9.5\%$  at Screening.
8. Uncontrolled hypothyroidism, including thyroid stimulating hormone (TSH)  $> 1.5 \times$  the upper limit of normal (ULN) at Screening.
9. Liver transplant and/or other significant liver disease or dysfunction including:
  - a. History of hepatic decompensation (such as ascites, variceal hemorrhage, hepatic encephalopathy, jaundice, and hepatorenal syndrome).
  - b. ALT or AST  $> 5 \times$  ULN, ALP  $> 2 \times$  ULN, or total bilirubin (TB)  $> 1.2 \times$  ULN at Screening. If TB is  $> 1.2 \times$  ULN, a reflex indirect (unconjugated) bilirubin will be obtained and if consistent with Gilbert's disease, in the opinion of the investigator, the subject may be enrolled in the study.
  - c. Positive serology for hepatitis B surface antigen (HBsAg) and/or hepatitis C virus antibodies (HCV Ab) at Screening.

Note: If test for hepatitis C antibody is positive, but optional unscheduled reflexive test for hepatitis C ribonucleic acid (RNA) is negative, subject can be enrolled.

- d. Presence or suspicion of other forms of chronic liver disease including alcoholic liver disease, hemochromatosis (ferritin  $> 1000$   $\mu\text{g/L}$  and percent iron saturation  $> 45\%$ ), Wilson's disease, known cirrhosis (i.e., historical liver biopsy with stage 4 fibrosis or equivalent, or any evidence of cirrhosis in the opinion of the investigator), autoimmune hepatitis, primary biliary cirrhosis, primary sclerosing cholangitis, drug-induced liver injury, and/or alpha-1 antitrypsin deficiency.
10. Human immunodeficiency virus (HIV) antibody positive.
11. Known hypersensitivity to HPG1860, the metabolites, or formulation excipient.

12. Significant gastrointestinal inflammation and symptoms including inflammatory bowel disease; Gastrointestinal conditions or procedures (including weight loss surgery; e.g., Lap-Band® or gastric bypass) that may affect drug absorption; planned weight reduction surgery during the study.
13. Hematologic or coagulation disorders, hemoglobin (Hgb) level  $<10.0$  g/dL (100 g/L), platelet count  $<100,000$  mm^3 or international normalized ratio (INR)  $\geq 1.2$  at Screening.
14. Unstable weight within the last 3 months of ( $>5\%$  change) at Screening.
15. Active malignancy, including those requiring surgery, chemotherapy, and/or radiation in the past 5 years. Nonmetastatic basal or squamous cell carcinoma of the skin and cervical carcinoma in situ are allowed.
16. Unexplained creatine kinase (CK)  $>3 \times$  ULN at Screening up to randomization (i.e., not associated with recent trauma or physically strenuous activity). Subjects with an explained CK elevation must have single repeat CK  $\leq 3 \times$  ULN prior to randomization.
17. History within the last 2 years of drug abuse including but not limited to, amphetamine and derivatives, or cocaine. Subjects with amphetamine derivatives prescribed by and under the care of a health care practitioner can be enrolled after evaluation by the investigator.
18. Blood donation, blood transfusion, participation in a clinical study with multiple blood draws, major trauma, or surgery with or without blood loss within 30 days prior to randomization and throughout the duration of study participation.
19. Use of any experimental or investigational drugs within 30 days prior to Screening.
20. Use of any of the following prior to Screening unless otherwise stated or a plan to use these drugs during the study is **prohibited**:
  - a. High-dose vitamin E ( $>400$  IU/day) (1 month prior to Screening).
  - b. Pioglitazone (3 months prior to Screening).
  - c. Medications associated with increased hepatic steatosis including mipomersen, lomitapide, amiodarone, methotrexate, tamoxifen, antiretrovirals, oral glucocorticoids at doses  $\geq 5$  mg

per day and/or valproic acid (3 months prior to Screening).

- d. Substrates for P-glycoprotein (P-gp) and/or breast cancer resistance protein (BCRP) including rosuvastatin (1 month prior to Screening) (Appendix 13).
21. Starting or adjusting the dose of the following permitted drugs within 5 weeks prior to Screening. These drugs are **allowed as long as stable** at least 5 weeks prior to Screening unless otherwise noted:
- a. Lipid regulating medications (except for rosuvastatin, which is prohibited) may be included; however, those that may affect liver steatosis or may have a potential drug-drug interaction risk are excluded per principal investigator (PI) discretion.
  - b. Hormone replacement.
  - c. Thyroid replacement.
  - d. Obesity medication (if dose is stable 6 months prior to Screening).
  - e. Diabetes medications (if dose is stable 3 months prior to Screening).
22. Unable to undergo or contraindication to MRI procedure (i.e., extensive tattoos, pacemaker, shrapnel injury, severe claustrophobia, ear (cochlea) implant).
23. History of intestinal resection or malabsorptive condition that may limit the absorption of HPG1860.
24. A medical or situational (i.e., geographical) finding that in the investigator's opinion may compromise the subject's safety or ability to complete the study.
25. An employee or contractor of the facility conducting the study, or a family member of the PI, co-investigator, or Sponsor.
26. Suspected Coronavirus Disease-19 (COVID-19) infection at Screening in the opinion of the investigator. COVID-19 screening is not required. During the study, if subjects have infections, the subjects may continue the study at the discretion of the PI. Subjects who receive COVID-19 vaccinations during the study are not excluded.
27. Any condition or finding that in the opinion of the PI or designee

would put the subject or study conduct at risk if the subject were to participate in the study.

28. Past 5 years history of bone disease disorder including osteoporosis

### **Investigational Medicinal Products**

- HPG1860 3 mg, 5 mg, and 8 mg capsules
  - Chemical name: (R)-2-(4-((5-cyclopropyl-3-(2,6-dichlorophenyl)isoxazol-4-yl)methyl)-2-methylpiperazin-1-yl)-4-methoxybenzo[d]thiazole-6-carboxylic acid
- Matching placebo capsules

All IMP will be ingested once daily at a similar time with or without food.

### **Statistical Procedures:**

#### **Sample Size**

A sample size of 17 in each group will provide 90% power to detect an absolute difference in mean CFB of 7.0% (a 33% reduction from baseline assuming a percent LFC value of 21.5% at baseline and 14.5% at Week 12) in at least 1 of the HPG1860 treatment groups compared to placebo using Dunnett's multiple comparisons test with a 2-sided significance level of 0.05 and assuming a common standard deviation of 6.8%. To account for a 15% dropout rate, approximately 20 subjects per group will be randomized.

#### **Analysis Populations**

The Intent-to-Treat (ITT) Population, used for all of the efficacy analyses, is defined as all randomized subjects. Subjects will be reported according to randomized study treatment.

The Per-Protocol (PP) Population, used for sensitivity analyses on the primary endpoint, is defined as all randomized subjects who received at least 80 to 120% of randomized treatment and had no major protocol deviations. Subjects will be reported according to randomized study treatment.

The Safety Population (SP), used for all of the safety summaries, is defined as all randomized subjects who received at least 1 dose of blinded IMP. Subjects will be reported according to actual treatment received at the first dose.

The PK Analysis Set (PKS), used for all of the PK-related summaries, is defined as all subjects in the SP who have at least 1 resulted PK assessment. Subjects will be reported according to actual treatment received at the first dose.

#### **Primary Safety Analysis**

Descriptive statistics will be used to assess the safety and tolerability

of 12-week treatment of HPG1860 3 mg, 5 mg, and 8 mg in subjects with NASH during the study. Safety assessments will include TEAEs including TEAEs of special interest, SAEs, changes in clinical safety laboratory values, 12-lead ECGs, and vital signs.

### **Efficacy Criteria for Evaluation**

Liver fat content and liver stiffness: Changes in LFC from baseline to Weeks 4 and 12 will be assessed by MRI-PDFF. All images will be approved by the central reader.

### **Key Secondary Efficacy Analysis**

The change in LFC measured by MRI-- PDFF from baseline to Week 12 will be analyzed using analysis of covariance (ANCOVA) adjusted for baseline LFC and treatment group. To control for multiple comparisons, Dunnett's test will be used to test if any of the treatment groups are significantly different from the placebo group.

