**Study Design:**

This is a Phase 2a, randomized, double-blind, placebo-controlled, parallel group, multiple arm, multicenter study of 3 different doses of HPG1860 versus placebo in subjects with biopsy-confirmed or phenotypic NASH. Screening will occur up to 5 weeks prior to randomization; all eligible subjects will have baseline hepatic imaging during Screening, prior to randomization. Approximately 80 eligible subjects will be randomized 1:1:1:1 on Day 1/Week 0 (T1) to receive either HPG1860 3 mg (n = 20), or 5 mg (n = 20), or 8 mg (n = 20), or placebo (n = 20) for 12 weeks. Following a preplanned interim analysis, a dose cohort may be dropped and/or added.

Randomized subjects will return for clinic visits at Week 2 (T2), Week 4 (T3), Week 8 (T4), and Week 12 (T5) as well as Week 16 (T6). Imaging procedures will be completed during Screening, Week 4 (T3), and Week 12 (T5). A follow-up visit will be completed 4 weeks after last dose of investigational medicinal product (IMP) at Week 16 (Visit T6).

At selected PK sites, serial PK samples will be collected from approximately 6 to 8 subjects in each dose cohort; blood samples will be collected on Day 1 pre-dose (within 30 minutes prior to dosing) and at 1, 2, 4, 6, and 8 hours ( $\pm 15$  minutes) post-dosing and on Day 14 pre-dose (within 30 minutes before dosing) and at 1, 2, 4, 6, and 8 hours ( $\pm 15$  minutes) post-dosing, and at 24 hours

(±30 minutes) prior to dosing on Day 15.

For all subjects, PK samples will be taken within 30 minutes prior to dosing at Weeks 4, 8, 12, and 16.

This study includes collection of reserve samples at Baseline (Day 1) and Week 12 for future biomarker analysis, unless prohibited by local law or regulations, and where approved by the Institutional Review Board (IRB).

**Duration of  
Treatment:**

Total study duration per subject: 21 weeks (approximate)

Screening: up to 5 weeks

Treatment: 12 weeks

Follow-up: 4 weeks

**Planned Sample Size  
and Treatment  
Groups:**

Planned: Approximately 80 adult male and female subjects

HPG1860 3 mg (n=20)

HPG1860 5 mg (n = 20)

HPG1860 8 mg (n = 20)

Placebo (n = 20)

Following a preplanned unblinded (comparative) interim analysis when 50% of randomized subjects have reached the Week 12 endpoint, an ongoing treatment group (3 mg, 5 mg, or 8 mg) may be dropped and/or a new treatment group of dose may be added.

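### As written, the Week 12 LFC ANCOVA has no missing-data rule, so it uses only subjects with a Week 12 scan, and the Week 4 scan does not inform the estimate

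*Combined protocol and SAP*

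**What the plan says.** All references are to the combined protocol and SAP.

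- **Analysis Populations:** "The Intent-to-Treat (ITT) Population, used for all of the efficacy analyses, is defined as all randomized subjects".
- **Key Secondary Efficacy Analysis:** the change in LFC to Week 12 "will be analyzed using analysis of covariance (ANCOVA) adjusted for baseline LFC and treatment group". For multiplicity, "Dunnett's test will be used to test if any of the treatment groups are significantly different from the placebo group". No imputation rule, missing-data assumption or estimand is attached.
- **Sample Size:** "A sample size of 17 in each group will provide 90% power to detect an absolute difference in mean CFB of 7.0" percentage points, with a common SD of 6.8. Then: "To account for a 15% dropout rate, approximately 20 subjects per group will be randomized".
- **Study Design:** LFC is imaged at Screening, Week 4 and Week 12.
- **Other Secondary Efficacy, Pharmacokinetic, and Pharmacodynamic Analyses:** the Week 4 change in LFC has its own ANCOVA, separate from the Week 12 model.
- **Sensitivity analysis:** the only one named uses the Per-Protocol Population. It is attached to the primary endpoint, which the objectives table defines as safety. It does not address missing Week 12 scans.

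**The concern.** An ANCOVA of change at one visit needs an outcome at that visit. Without imputation, a subject who has no Week 12 scan leaves the model. The set analysed is then those scanned at Week 12, whereas the plan describes it as everyone randomized.

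The plan expects about 15% dropout, and some of those who leave will already have a Week 4 scan on the same scale. Nothing links that scan to the Week 12 estimate.

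Two things are at stake. If dropout is related to early LFC response, and differently so in the active and placebo arms, the Week 12 contrast is biased. Some precision is also lost, in a trial sized on 17 evaluable subjects per arm. This is the key efficacy comparison, and the text supplied would leave the handling of missing scans to be settled after data have been seen.

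**Working it through.** **1. The plan's own figure.** Inputs from Sample Size: difference 7.0, SD 6.8, two-sided 0.05, Dunnett, at least one of three doses significant. A simulation of the Dunnett test with all three doses at 7.0 gives 89.0% power at n = 16 and 90.9% at n = 17, so 17 is the smallest n that reaches 90%. Inflation: 17/0.85 = 20. The stated figures reproduce.

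**2. Subjects outside the model.** 20 × 0.15 = 3 per arm, so 4 × 3 = 12 of 80.

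**3. Assumptions.** The documents do not give the Week 4–Week 12 correlation (ρ), the dropout mechanism or dropout by arm. I take SD 6.8 at both visits, ρ from 0.5 to 0.8, and no baseline adjustment. Let e4 be the standardised Week 4 change around the subject's own arm mean (higher is worse), with logit P(dropout) = a + 1.5·e4 and a set to give the stated rate.

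**4. Bias of the ANCOVA as written.** Bias = ρ × 6.8 × [mean e4 of those staying on active − mean e4 of those staying on placebo].

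For 20% against 10% dropout the two means are −0.227 and −0.122, a difference of −0.105:
- ρ = 0.5: 0.5 × 6.8 × (−0.105) = −0.36, an estimate of about −7.4.
- ρ = 0.8: 0.8 × 6.8 × (−0.105) = −0.57, an estimate of about −7.6.

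| Assumed dropout | ANCOVA bias, ρ 0.5 to 0.8 |
|---|---|
| 20% active, 10% placebo, slope 1.5 | −0.36 to −0.57 |
| Same rates, slope halved to 0.75 | −0.23 to −0.36 |
| 25% active, 5% placebo, slope 1.5 | −0.72 to −1.15 |
| Same absolute Week 4 response drives dropout in every arm, half the effect present by Week 4 (about 11% active, 19% placebo) | +0.27 to +0.43 |
| 15% in both arms, same dependence on e4 | 0 |

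A negative bias overstates the drug effect and a positive one understates it.

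**5. Estimate using Week 4.** With monotone missing data, the MMRM with unstructured covariance estimates each arm's Week 12 mean as the mean of those scanned at Week 12 plus b × (Week 4 mean of all scanned at Week 4 − Week 4 mean of those also scanned at Week 12), where b is the slope of Week 12 on Week 4. Its bias is 0 in every row above, but only because dropout there depends on Week 4 alone and every dropout has that scan. Relaxing this, with dependence in the active arm only (slope 1.2, about 15% overall dropout):

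| Situation | ANCOVA | With Week 4 |
|---|---|---|
| Week 4-driven, ρ 0.7, all dropouts have a Week 4 scan | −0.74 | 0.0 |
| Same, half of the dropouts have one | −0.76 | −0.35 |
| Same, none has one | −0.77 | −0.77 |
| Driven by the unseen Week 12 value, ρ 0.3 | −1.08 | −0.99 |
| Same, ρ 0.85 | −1.08 | −0.32 |

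In these runs placebo dropout is 15% and active about 2 × 15.4 − 15 = 15.8%. Near-equal rates do not prevent bias if the mechanism differs by arm.

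**6. Precision with random, equal 15% dropout.** Effective n = 1/[(1 − ρ²)/17 + ρ²/20].
- ρ = 0.5: 1/(0.75/17 + 0.25/20) = 17.7.
- ρ = 0.8: 1/(0.36/17 + 0.64/20) = 18.8.

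The standard error of a dose–placebo difference at 17 per arm is 6.8 × √(2/17) = 2.33. It falls by 2% (√(17/17.7) = 0.98) to 5% (√(17/18.8) = 0.95).

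**The case against.** **The bias is small and hypothetical.** No passage ties withdrawal to Week 4 LFC, and the plan gives a single dropout rate. A shift of 0.4 to 0.6 is about a quarter of one standard error or less (0.57/2.33 = 0.24). This stands: the figures show sensitivity to assumptions and do not forecast the trial's bias.

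**The precision gain is modest.** Any-pair power rises from 90.9% to 91.9% at ρ = 0.5, and only to 93.7% at ρ = 0.85. LFC is a key secondary endpoint in a phase 2a safety trial, and baseline-adjusted ANCOVA is a standard method. This also stands.

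**The text is a synopsis.** A missing-data section may exist elsewhere. That would answer the first half of the point, and the synopsis should then agree with it.

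A reader might infer three stronger claims that the documents do not support:

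- *That ANCOVA can use only completers.* A subject off treatment but scanned at Week 12 is included, and ANCOVA with multiple imputation can include everyone randomized. The gap is the missing rule.
- *That a repeated-measures model keeps all dropouts.* Week 4 is the only earlier post-baseline scan. Those who leave before it add nothing to the MMRM, whose analysis set is then also smaller than all randomized.
- *That it removes the bias, or that the bias must favour the drug.* The tables in the working show neither is generally true.

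**Conclusion.** The point holds in limited form. The supplied text gives no missing-data handling for Week 12 LFC, so its analysis set does not match its ITT definition, and it leaves Week 4 data out of the Week 12 estimate.

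Under assumed 20% against 10% dropout related to Week 4 response, the bias is about 0.4 to 0.6 LFC points on a true 7.0, and its direction depends on the mechanism. It is zero when equal 15% dropout follows the same mechanism in both arms. Using Week 4 reduces bias from dropout related to Week 4 response. It removes that bias only under missing at random and when the dropouts have a Week 4 scan.

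The precision gain, to an effective n of about 17.7 to 18.8 per arm, assumes ρ of 0.5 to 0.8 and a Week 4 scan for every dropout. The stated sample size is not in error on its own definition of power. The main reason to act is the unstated assumption; the gain in power is secondary.

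**What to change.** In Key Secondary Efficacy Analysis:

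1. State the estimand and the missing-data assumption for Week 12 LFC, and say how randomized subjects with no post-baseline scan are handled.
2. Analyse change in LFC at Weeks 4 and 12 in one MMRM: treatment, visit, treatment-by-visit, baseline LFC, baseline-by-visit, unstructured covariance, Kenward-Roger degrees of freedom. Alternatively, use ANCOVA with multiple imputation that includes Week 4 LFC; this can cover everyone randomized.
3. Apply the Dunnett adjustment to the three Week 12 dose–placebo contrasts.
4. Keep the ANCOVA on subjects with a Week 12 scan as supportive. It does not by itself test the missing-data assumption.
5. Add a delta-adjusted or reference-based sensitivity analysis for departures from missing at random.

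Settle this before the unblinded interim analysis described under Study Design, so that the choice cannot depend on results. The cost is SAP wording and a modest amount of programming, with no new scans. The downside is reliance on missing at random, which item 5 is there to probe.

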### Secondary Objectives and Endpoints

	
imaging-proton density fat fraction (MRI-PDFF) at Week 12
 
Other Secondary Endpoints:
 
 
Percentage of subjects with <math>\geq 30\%</math> reduction in LFC from baseline measured by MRI-PDFF at Week 4 and Week 12
 
CFB in LFC as measured by MRI-PDFF at Week 4
 

 
To evaluate the pharmacokinetic (PK) profile of HPG1860 in NASH patients
 
	
PK Endpoints including:
 
 
Area under the curve from time zero to infinity (<math>AUC_{0-\infty}</math>), AUC from time zero to the time of the last quantifiable concentration (<math>AUC_{0-t}</math>), AUC during the 24- hour dosing interval (<math>AUC_{0-24h}</math>), maximum observed concentration (<math>C_{max}</math>), time to maximum plasma concentration (<math>T_{max}</math>), half-life (<math>T_{1/2}</math>), apparent total clearance of the drug from plasma after oral administration (CL/F), and apparent volume of distribution during terminal phase after extravascular administration (<math>V_z/F</math>)
 
Trough concentration (<math>C_{trough}</math>)
 
Accumulation ratio (<math>R_{ac}</math>) based on <math>C_{max}</math> and AUC
 

 
To evaluate the effect of HPG1860 compared to placebo on biomarkers of interest
 
	
 
CFB in insulin, fasting plasma glucose (FPG) and homeostatic model assessment of insulin resistance (HOMA-IR) at Weeks 8, 12, and 16. Note:
 

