- Phenotypic diagnosis based on the following: liver stiffness  $\geq 8.0 \text{ kPa}$  and controlled attenuation parameter (CAP)  $> 300 \text{ dB/m}$  on transient elastography (TE) OR

- Elevated ALT (males >40 IU/L, females >30 IU/L), BMI  $\geq 27$  kg/m^2, and diagnosis of type 2 diabetes mellitus (T2DM).
7. Subjects will have CAP >300 dB/m on TE at screening and hepatic fat assessed by a central reader of MRI-PDFF  $\geq 10\%$  during Screening.
  8. Male subjects must refrain from sperm donation from Screening through at least 90 days following the last dose of IMPs.
  9. Female subjects must refrain from egg donation or harvest for 30 days after last dose of IMPs.
  10. Willing and able to adhere to study restrictions and agree to comply with study protocol.

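### Minor: the plan names no T2DM stratum and no analysis by T2DM status, so with 20 per arm a chance difference in diabetes mix could blur the glycaemic comparisons; the remedy is cheap

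*Combined protocol and SAP*

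**What the plan says.** - **Population.** Inclusion criterion 6 accepts any one of three definitions of NASH. One combines raised ALT and a BMI threshold with a "diagnosis of type 2 diabetes mellitus (T2DM"); the biopsy and elastography definitions do not require diabetes. The exclusion criteria rule out T2DM only when uncontrolled, and they permit diabetes drugs at a stable dose. The sample will therefore be mixed, and T2DM status can be recorded before Day 1.
- **Randomization.** Study Design states: "Approximately 80 eligible subjects will be randomized 1:1:1:1 on Day 1/Week 0 (T1"). No stratification factor is named there or elsewhere.
- **LFC analysis.** Key Secondary Efficacy Analysis specifies an ANCOVA "adjusted for baseline LFC and treatment group", with Dunnett's test for the comparisons with placebo. The Week 4 LFC analysis uses the same approach.
- **Glycaemic endpoints.** Secondary Objectives and Endpoints lists change from baseline in insulin, FPG and "homeostatic model assessment of insulin resistance (HOMA-IR") at Weeks 8, 12 and 16, under an objective that compares HPG1860 with placebo. The section on other secondary analyses plans only summaries of values and changes for the metabolic biomarkers. It gives no model, no adjustment and no breakdown by T2DM.

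**The concern.** Diabetes status is the baseline factor most plausibly tied to how glucose, insulin and HOMA-IR move over 12 to 16 weeks. If one dose arm happens to hold clearly more or fewer subjects with T2DM than placebo, the arm summaries mix any drug effect with the difference in diabetes mix. The planned tables give no means of separating the two. For LFC, T2DM may also explain some variation beyond baseline LFC, which the model would leave in the residual. What is at stake is the interpretation of three secondary endpoints and a little precision on the key secondary endpoint. The validity of the trial is not in question.

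**Working it through.** **1. The plan's own figure.** Sample Size states: "A sample size of 17 in each group will provide 90% power" to "detect an absolute difference in mean CFB of 7.0" points "in at least 1 of the HPG1860 treatment groups compared to placebo", "using Dunnett's multiple comparisons test with a 2-sided significance level of 0.05", with SD 6.8. A simulated Dunnett test (three doses against one control, 64 degrees of freedom, critical value about 2.41), with all three doses at 7.0 points, gives 90.8% power. Dropout: 17 / (1 − 0.15) = 20. Both figures reproduce. If only one dose works, the power for that specified comparison is 72.2%.

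**2. Chance imbalance in T2DM.** Inputs: 20 per arm (Study Design) and an assumed T2DM share p of 30–70%. The SD of the difference in T2DM share between two arms is √(2p(1 − p)/20).
- p = 0.3 or 0.7: √(2 × 0.21 / 20) = 14.5 points.
- p = 0.5: √(2 × 0.25 / 20) = 15.8 points.

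The one-dose column below uses two independent binomial counts (exact). The other column is a simulation of the largest of the three dose–placebo gaps.

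| Gap in T2DM share | One named dose vs placebo | At least one of three doses |
|---|---|---|
| 20 points or more (4 subjects) | 23–27% | 48–55% |
| 30 points or more (6 subjects) | 6–8% | 14–19% |

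**3. Effect on glycaemic change.** Shift in the dose–placebo difference = gap × difference in mean change by T2DM status. The documents do not give the second factor. For each 10 mg/dL by which mean FPG change differs between subjects with and without T2DM, the shift is 0.20 × 10 = 2 mg/dL at a 20-point gap and 0.30 × 10 = 3 mg/dL at a 30-point gap.

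**4. Effect on LFC.** Assume that mean LFC change differs by δ = 1 to 4 points by T2DM status.
- 20-point gap: 0.20 × 1 = 0.2 to 0.20 × 4 = 0.8 points.
- 30-point gap: 0.30 × 1 = 0.3 to 0.30 × 4 = 1.2 points, which is 4–17% of 7.0.
- Standard error of a dose–placebo difference: 6.8 × √(2/17) = 2.33 points. The largest of these shifts is 1.2 / 2.33 = 0.51 standard errors.

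**5. Gain or loss from a T2DM term in the LFC model.** Share of variance explained at a 50% T2DM share = 0.25δ² / 6.8², that is 0.5%, 2.2%, 4.9% and 8.7% for δ = 1, 2, 3 and 4. With 68 evaluable subjects, residual degrees of freedom fall from 63 to 62, and 63/62 = 1.016. The net change in residual variance is then +1.6% at δ = 0, and +1.1%, −0.6%, −3.3% and −7.2% for δ = 1 to 4.

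Simulated ANCOVA with Dunnett (17 per arm, one effective dose, T2DM share 50%, 10,000 trials per case):

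| δ | Power without T2DM term | Power with T2DM term |
|---|---|---|
| 0 | 71.2% | 70.3% |
| 2 | 71.9% | 71.9% |
| 4 | 71.2% | 74.7% |

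With no dose effect, the familywise error is 0.051–0.052 without the term and 0.051–0.053 with it.

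**The case against.** The opposing case is strong on several points, and they limit what can be claimed.

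- **Bias.** A reader might infer that an imbalance biases the comparisons. It does not. Chance imbalance is part of the sampling variation that the standard error already covers, and the familywise error stays near 5% with or without a T2DM term. This objection stands in full.
- **The ANCOVA and the glycaemic endpoints.** A reader might infer that leaving T2DM out of the ANCOVA is what leaves FPG, insulin and HOMA-IR uncorrected. That model applies only to LFC, and the glycaemic endpoints have no model at all. A T2DM term in the LFC model does nothing for them; stratification and a breakdown by T2DM status do.
- **ALT.** A reader might extend the point to ALT because the T2DM entry route also requires raised ALT. A subject with T2DM can enter by biopsy or elastography with normal ALT, so T2DM status does not mark the ALT-selected route. Baseline ALT would be the natural adjustment.
- **No strata.** The text is a synopsis and does not describe the randomization method. It supports saying that no factor is named, and not that none is used.
- **Size.** The glycaemic endpoints are changes from baseline, so differences in level are subtracted. The HbA1c limit and the stable-dose rule also restrain drift. How far mean change differs by T2DM status is unknown, and the LFC gain is visible only at the largest assumed effect.

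What remains is that a sizeable imbalance is a realistic prospect, the plan gives no way to see past it in the glycaemic tables, and the remedy uses information available before randomization.

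**Conclusion.** The point holds as a minor, low-cost improvement. With 20 per arm, it is roughly an even chance that at least one dose arm differs from placebo by 20 or more points in T2DM, and about one in four for any given dose. The consequence is some lost precision, and glycaemic comparisons that cannot be read apart from diabetes mix. For LFC the consequence is small: at most about half a standard error at a 30-point gap, and between 0.9 points of power lost and 3.5 gained from adding the term. These figures rest on an assumed T2DM share of 30–70% (50% for the power runs) and an assumed T2DM effect on LFC change of 0–4 points. The documents give neither. Nothing here changes the planned sample size.

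**What to change.** 1. In Study Design, state whether randomization is stratified, and stratify by T2DM (yes/no).
2. In Key Secondary Efficacy Analysis, and in the matching Week 4 analysis, add T2DM status to treatment group and baseline LFC, so that the model follows the randomization.
3. Present change in FPG, insulin and HOMA-IR by T2DM status as well as overall.
4. If randomization has already started unstratified, keep the by-T2DM glycaemic summaries and the prespecified covariate.

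The cost is one two-level stratum in the randomization system, one model term and one split of the glycaemic tables, with no added subjects or procedures. If T2DM is unrelated to LFC change, the term costs one degree of freedom, about 1–2% of variance and under 1 point of power. If its effect is 4 points, it gains about 3.5 points of power. Central blocks of four within each stratum would hold arms to within one T2DM subject at randomization (1/20 = 5 points). That balance will loosen after the expected 15% dropout, or if an arm is dropped or added at the interim analysis.
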